Appendix 5 Toxicity Grading Scale for Laboratory Values

Toxicity Grading Scale ^a for Laboratory Values					
Parameter		Grade ^b			
		1	2	3	4
Haematology					
Hgb	Decrease	<LLN – 10 g/dL	<10 – 8 g/dL	<8.0 g/dL	
	Increase	>0 – 2 g/dL above ULN	>2 – 4 g/dL above ULN	>4 g/dL above ULN	
WBC	Decrease	<LLN – 3000/mm ³	<3000 – 2000/mm ³	<2000 – 1000/mm ³	<1000/mm ³
	Increase			>100000/mm ³	
Platelets (decreased)		<LLN – 75000/mm ³	<75000 – 50000/mm ³	<50000 – 25000/mm ³	<25000/mm ³
Clinical chemistry					
Calcium (high)		>ULN – 2.9 mmol/L	>2.9 – 3.1 mmol/L	>3.1 – 3.4 mmol/L	>3.4 mmol/L
Calcium (low)		<LLN – 2.0 mmol/L	<2.0 – 1.75 mmol/L	<1.75 – 1.5 mmol/L	<1.5 mmol/L
Sodium (high)		>ULN – 150 mmol/L	>150 – 155 mmol/L	>155 – 160 mmol/L	> 160 mmol/L
Sodium (low)		<LLN – 130 mmol/L		<130 – 120 mmol/L	<130 – 120 mmol/L
Potassium (high)		>ULN – 5.5 mmol/L	>5.5– 6.0 mmol/L	>6.0 – 7.0 mmol/L	>7.0 mmol/L
Potassium (low)		<LLN – 3.0 mmol/L	<LLN – 3.0 mmol/L	<3.0 – 2.5 mmol/L	<2.5 mmol/L
Albumin		<LLN – < 3 g/dL	<3 – 2 g/dL	<2 g/dL	
ALT		>ULN – 3.0 × ULN	>3.0 – 5.0 × ULN	>5.0 – 20.0 × ULN	>20.0 × ULN
Aspartate aminotransferase		>ULN – 3.0 × ULN	>3.0 – 5.0 × ULN	>5.0 – 20.0 × ULN	>20.0 × ULN
Total bilirubin		>ULN – 1.5 × ULN	>1.5 – 3.0 × ULN	>3.0 – 10.0 × ULN	>10.0 × ULN
ALP		>ULN – 2.5 × ULN	>2.5 – 5.0 × ULN	>5.0 – 20.0 × ULN	>20.0 × ULN

Toxicity Grading Scale^a for Laboratory Values				
Parameter	Grade^b			
	1	2	3	4
Creatinine	>ULN – 1.5 × ULN	>1.5 – 3.0 × ULN	>3.0 – 6.0 × ULN	>6.0 × ULN
INR	>1 – 1.5 × ULN	>1.5 – 2.5 × ULN	>2.5 × ULN	
aPTT	>ULN – 1.5 × ULN	>1.5 - 2.5 × ULN	>2.5 × ULN	

ALT=alanine aminotransferase; ALP=alkaline phosphatase; aPTT=activated partial thromboplastin time; CTCAE=Common Terminology Criteria for Adverse Events; HgB=haemoglobin; INR=international normalised ratio; LLN=lower limit of normal; ULN=upper limit of normal; WBC=white blood cell.

^aThe National Cancer Institute CTCAE v4.03.

^bGrade refers to severity: 1=mild, 2=moderate, 3=severe, 4=life-threatening or disabling, 5 (not shown in the table)=death.

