6.8.3 Toxicity Grading Scale

Laboratory values will be evaluated according to the CTCAE Version 4.03 toxicity grading scale and captured on the eCRF by the investigator. Grades 3 and 4 will be considered AEs and reported appropriately. The laboratory parameters and the corresponding grading scale are provided in [Appendix 5](#). Laboratory parameters not covered by the CTCAE toxicity scale will be evaluated according to normal values assigned by the local laboratory.

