6.13.7 Clinical Laboratory Adverse Events

The investigator's assessment of each relevant laboratory value will be recorded on the eCRF. For each abnormal laboratory value, the investigator will determine whether the value is considered clinically significant or not. For clinically significant values, the investigator will indicate if the values constitute a new AE and record the sign, symptom, or medical diagnosis on the AE eCRF. The investigator will also record on the AE eCRF

whether the clinically significant values are symptoms or related to previously recorded AEs, are due to pre-existing diseases, or are due to other issues. Adverse events that are grade 3 and 4 will be considered AEs and reported appropriately. The laboratory parameters and the corresponding grading scale are provided in [Appendix 4](#). Additional tests and other evaluations required to establish the significance or aetiology of an abnormal value or to monitor the course of an AE should be obtained when clinically indicated. Any abnormal value that persists should be followed at the discretion of the investigator.

Any seroconversion result for HIV, HAV, HBV, HCV, hepatitis E virus (HEV), or parvovirus B19 (B19V) shall be re-tested.

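### The low-sodium row in Appendix 5 prints one range for both Grade 3 and Grade 4, so values below 120 mmol/L have no grade and miss the automatic AE trigger

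*Protocol*

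**What the plan says.** The low-sodium row of protocol Appendix 5 reads as follows:

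- Grade 1: "<LLN – 130 mmol/L"
- Grade 2: blank
- Grade 3: "<130 – 120 mmol/L"
- Grade 4: the same entry as Grade 3

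The footnotes name CTCAE v4.03 as the source and define the upper grades as "3=severe, 4=life-threatening or disabling".

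Section 6.8.3 sets the rule that uses these grades: "Laboratory values will be evaluated according to the CTCAE Version 4.03 toxicity grading scale", the investigator records the result on the eCRF, and "Grades 3 and 4 will be considered AEs and reported appropriately". Both that section and section 6.8.1 send the reader to Appendix 5 for the scale. Section 6.13.7 repeats the Grade 3 and 4 rule but points to Appendix 4, which lists tests and visit times and contains no grading scale.

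Section 6.13.7 also gives a route to an AE that does not depend on grade: "For each abnormal laboratory value, the investigator will determine whether the value is considered clinically significant or not". A clinically significant value is then assessed as a possible new AE.

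**The concern.** Two grades with different meanings should not share one range, and the bottom of a low-value scale should not be left open. As printed, the row does both. A sodium of 125 mmol/L is both severe and life-threatening. A sodium of 115 mmol/L, which is further from normal, is neither.

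This matters because the table feeds a reporting rule. Section 6.8.3 is written so that a Grade 3 or 4 value becomes an AE without further judgement, and Appendix 5 is the scale sites are told to use. A value with no grade cannot set off that rule. Appendix 4 schedules sodium at screening, at the Day 5 or pre-discharge visit, at Day 30 and at unscheduled visits, so the row will be used after surgery.

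**Working it through.** No sample-size, power or alpha figure is involved. The check is whether the printed ranges cover every low value exactly once.

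**Inputs.** All ranges come from Appendix 5. An entry of the form 'below a, down to b' is read as b ≤ value < a. The table gives no number for the lower limit of normal (LLN). I assumed 135 mmol/L; this affects only the upper edge of Grade 1 and nothing below 130.

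**Step 1: grade some test values from the row as printed.**

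| Sodium (mmol/L) | Grades that fit |
|---|---|
| 134 | 1 |
| 130 | 1 |
| 129.9 | 3 and 4 |
| 125 | 3 and 4 |
| 120 | 3 and 4 |
| 119.9 | none |
| 115 | none |
| 110 | none |

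The overlap is the whole band from 120 to below 130. The gap is everything below 120.

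**Step 2: compare with the other rows that print a Grade 4 entry.** There are 13 such rows. For each, the table below sets the end of Grade 3 beside the start of Grade 4.

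| Row | Grade 3 ends | Grade 4 starts |
|---|---|---|
| WBC decrease (/mm³) | 1000 | 1000 |
| Platelets (/mm³) | 25000 | 25000 |
| Calcium high (mmol/L) | 3.4 | 3.4 |
| Calcium low (mmol/L) | 1.5 | 1.5 |
| Sodium high (mmol/L) | 160 | 160 |
| **Sodium low (mmol/L)** | **120** | **130** |
| Potassium high (mmol/L) | 7.0 | 7.0 |
| Potassium low (mmol/L) | 2.5 | 2.5 |
| ALT (× ULN) | 20 | 20 |
| Aspartate aminotransferase (× ULN) | 20 | 20 |
| Total bilirubin (× ULN) | 10 | 10 |
| ALP (× ULN) | 20 | 20 |
| Creatinine (× ULN) | 6 | 6 |

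Twelve of 13 meet exactly. High sodium is the nearest comparison: its Grade 3 is ">155 – 160 mmol/L" and its Grade 4 is everything above 160. The rows with no Grade 4 entry (haemoglobin decrease and increase, WBC increase, albumin, INR, aPTT) have an open-ended Grade 3, so they leave no gap at the extreme. Low sodium is the only row whose extreme values have no grade.

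**Step 3: apply the rule in section 6.8.3.**

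- From 120 to below 130: Grade 3 or Grade 4, so an AE either way. Only the grade is undetermined.
- Below 120: no grade, so the rule does not operate.

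**Step 4: illustrate a consistent row.** If Grade 4 began where Grade 3 ends, as in the other 12 rows, 120 to below 130 would be Grade 3 alone and every value below 120 would be Grade 4. Gap and overlap would both close. This shows the table's own pattern; the actual entry has to come from the source the table cites.

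**The case against.** **The text may have been misread.** The table reached this review by machine reading, and a misread Grade 4 cell cannot be excluded. Against that, the blank Grade 2 cell in the same row survived, as did blanks in other rows. A single merged cell across Grades 3 and 4 would still leave values below 120 uncovered. The doubt stands to this extent: the source page must be checked first.

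**Severe hyponatraemia would go unreported.** A reader might infer this, and the documents do not support it. CTCAE v4.03 is named both in section 6.8.3 and under the table, so a site can resolve the cell from that scale. Section 6.13 counts an abnormal laboratory finding as a possible AE, and section 6.13.7 has the investigator judge every abnormal value whatever its grade. A value below 120 is lost from the AE record only if the site takes the table literally and the investigator also judges the value not clinically significant. Only the automatic trigger is lost.

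**A safety endpoint or a planned table would change.** A reader might infer this too, but it is not shown. The protocol lists laboratory values as a safety endpoint, not CTCAE grades. SAP section 11 summarises absolute values and changes from baseline, builds its shift tables on normal, abnormal/not clinically significant and abnormal/clinically significant, and grades AE severity as mild, moderate or severe. No planned table separates CTCAE Grade 3 from Grade 4. A sodium below 120 would still enter the chemistry summary if taken at a scheduled visit, and the SAP also plans a listing of abnormal chemistry values.

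**Low potassium has the same fault.** That row also repeats a range, under Grades 1 and 2. The repeat leaves no value without a grade and does not touch the Grade 3 and 4 rule, so it forms no part of this point.

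**Conclusion.** The point holds as an internal error in one row of a table that sites use to decide what is an AE. As printed, every sodium value below 120 mmol/L is ungraded and every value from 120 to below 130 carries two grades. The first takes the lowest values out of the automatic rule in section 6.8.3; the second leaves AE status unchanged but removes the line between severe and life-threatening.

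The size is small. The documents give no expected frequency of such values, so the number of patients affected cannot be estimated. Other routes to AE capture remain, and the primary endpoint, sample size, alpha and planned SAP tables are untouched. It is worth correcting because a rule meant to work without judgement should not fall back on judgement at its most extreme values.

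The conclusion assumes that the source page prints the row as it was read here. It does not depend on the value taken for the LLN.

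**What to change.** 1. Check the low-sodium row on the source page of Appendix 5.
2. If it reads as above, reconcile the row with the CTCAE version the table cites, so that Grades 3 and 4 do not overlap and no low value is left without a grade.
3. Check any eCRF grading or site worksheet built from the table, and re-grade sodium values below 130 mmol/L already recorded under it.
4. In the same edit, point section 6.13.7 to Appendix 5, where the scale is.

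The cost is one table entry and one cross-reference in the protocol, plus a check of the eCRF if grading was programmed from the table. No analysis in the SAP has to be changed.

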Appendix 6 Instructions for Preparation of FS VH S/D 500 s-apr

The shelf life of FS VH S/D 500 s-apr (frozen) in AST is 24 months, provided that the product is shipped and stored at $\leq -4^{\circ}\text{F}$ (-20°C). Thawed, unopened pouches may be stored for up to 4 hours in an incubator at 98.6°F (37°C) until use. If the solution is not used within 4 hours after thawing, FS VH S/D 500 s-apr must be discarded.

Pre-filled syringes are for single use only. Discard any unused product.

The product must not be used after the expiration date indicated on the label.

Procedure for thawing FS VH S/D s-apr (frozen) using incubator (98.6°F [37°C]):

On Day 0 (surgery day), keep the pre-filled syringes in their pouches and place them in an incubator. Remove the pouches from the incubator after thawing and warming. Transfer the inner pouch with the pre-filled syringe onto the sterile field. Maintain the product at 98.6°F (37°C) until use. The product must be used within 4 hours. (*The protective syringe cap should not be removed until thawing is complete and the application tip is ready to be attached*).

Approximate Incubator Thawing and Warming Times	
Incubator (in pouches) at 98.6°F (37°C)	
Pack Size	Advanced Syringe Technology (AST)
4 mL	85 minutes

The sealer protein and the thrombin solutions should be clear or slightly opalescent. Do not use solutions that are cloudy or have deposits. Before use, check the thawed product visually for particles, discoloration, or other changes in its appearance. If one of the above occurs, dispose of the solutions.

The thawed sealer protein solution should be liquid but slightly viscous. If the solution has the consistency of a solidified gel, it must be assumed to have become denatured (possibly due to an interruption of the cold storage chain or by overheating during warming). In this case, do not use FS VH S/D 500 s-apr on any account!

Remove the syringe from the bags only shortly before use. Remove the protective caps from the syringes only immediately before application. Use FS VH S/D 500 s-apr only when it is thawed and warmed completely (liquid consistency).

Important Notes:

- Do not use FS VH S/D 500 s-apr (frozen) unless it is completely thawed and warmed (liquid consistency) to 98.6°F (37°C).
- Do not thaw the product by holding it in your hands!²⁵
- Do not expose to temperatures above 98.6°F (37°C).
- Do not microwave.
- Once thawed, do not refrigerate or re-freeze.

Application:

For application, connect the double chamber ready-to-use syringe with the sealer protein solution and the thrombin solution to a joining piece and an application canula – both are provided in the set with the application devices. The common plunger of the double chamber ready-to-use syringe ensures that equal volumes of the two sealant components are fed through the joining piece into the application canula where they are blended and then applied.

FS VH S/D 500 s-apr is to be applied by dripping in a thin and continuous layer with a 5 mm overlap on each side of the sutured line. Approximately 2 mL of FS VH S/D 500 s-apr will be needed to cover a suture line 10 cm long and a 1 cm wide (10 cm²) as per the package insert. Keep the dura surface that is adjacent to the suture as dry as possible immediately before and during the application of the IP. In order to ensure adequate mixing, immediately before application, expel the first 5 drops from the syringe, then apply product along the dura suture line. Keep the application speed as constant as possible (ie, 0.5 mL/second). In case the second application is needed, all polymerized product from the first application must be removed before the second application is done.

Appendix 7 Instructions for Preparation of DuraSeal Dural Sealant

The shelf life of DuraSeal Dural Sealant is 12 months, provided that the product is shipped and stored at 77°F (25°C).²⁷ Application of DuraSeal hydrogel must be completed within 1 hour after preparation. The DuraSeal Dural Sealant System is for single use only. Discard any unused product.

How Supplied

The components of the DuraSeal System are:

Diluent Syringe (blue label) with white cap (1)	Spray Tip (3)
Powder Vial (1)	Plunger Cap (1)
Clear Precursor Syringe with white cap (1)	Syringe Holder (1)
Applicator (1)	

Directions for Use:

The application procedure consists of 3 steps:

- A) Preparing the Blue Precursor,
- B) Assembling the DuraSeal System Applicator; and
- C) Hydrogel Application.

Preparing the Blue Precursor:

Note: Inspect the PEG powder vial to ensure the powder is free-flowing, or can be loosened up by shaking. If the powder remains not free-flowing, discard the entire kit.

1. Open the pouch and introduce the polymer kit tray into the sterile field.
 2. Once in the sterile field, remove the lid from the polymer kit tray.
 3. Remove and discard syringe cap from Diluent Syringe (blue label).
 4. Attach the Diluent Syringe to the Powder Vial.
 5. Without depressing the syringe plunger, pierce the vial seal by pushing the syringe into the vial cap until it is fully depressed (twisting is not required). The entire threaded
-
- 

portion of the vial cap should be depressed below the level of the surrounding plastic vial rim.

6. Inject syringe contents into the vial.
7. Gently shake the vial/syringe assembly until the powder is completely dissolved. The solution will turn blue.
8. Invert the vial/syringe assembly, and draw the vial contents back into the syringe.
9. Unscrew the syringe from the vial and discard the vial.

Assembling the DuraSeal System Applicator

1. Prior to attaching the syringes to the applicator, ensure syringe fluid levels are equal. If fluid levels are not equal, expel fluids out of syringes until equal.
2. Attach blue and clear precursor syringes to the applicator.
3. Attach the syringe holder which slides over both syringe barrels.
4. Carefully attach the Plunger Cap to the plungers of both syringes without dispensing precursors into the applicator. Hold the syringes by the plungers while performing this operation so as to not deliver any of the precursors into the applicator.
5. Attach a spray tip to the applicator.

Note: Avoid touching the Plunger Cap before application to avoid inadvertent precursor injection and tip plugging.

Hydrogel Application

Note: Achieve hemostasis and minimize CSF outflow. Ensure that there are 2 - 3 mm margins around the durotomy edge and that the margins are clear of clots and fluids, hemostatic agents and loose connective tissue.

1. Position the applicator 2 - 4 cm from the target site. Apply firm even pressure to the center of the Plunger Cap to dispense the precursors. Rapid initial spraying, followed by a slower controlled rate is recommended.
 2. Continue applying the hydrogel until a thin (1 – 2 mm) coating is formed.
-
- 

Note: If delivery is interrupted and the spray tip is plugged, remove the spray tip, wipe the applicator tip, attach a new spray tip, and continue delivery.

Note: The blue colour of the hydrogel aids in gauging thickness. As the thickness of the DuraSeal hydrogel increases to 2 mm, the fine epidural vasculature becomes less visible.

Note: Hydrogel application beyond the edges of the dural margin may be removed with scissors or mechanical disruption. Irrigation immediately after the sealant has solidified is permitted.

Storage

The DuraSeal Dural Sealant System should be stored at or below 77°F (25°C).

Appendix 8 Surgical Site Infections (SSIs) – CDC/NHSN Definitions

In this protocol, SSIs will be defined according to the criteria outlined by the CDC and the NHSN (in table below) modified to fit this protocol from www.cdc.gov/nhsn/PDFs/pscManual/9pscSSIcurrent.pdf.³²

Surgical site infections are divided into 1 of the following types:

1. Superficial incisional SSIs
2. Deep incisional SSIs
3. Organ/space SSIs

Surgical Site Infections – CDC/NHSN Definitions	
Superficial incisional SSI	
Superficial incisional SSIs must meet the following criteria:
 
Infection occurs within 30 days after the operative procedure (where Day 1 = the procedure date)
 
And
 
Involves only skin and subcutaneous tissue of the incision
 
And
 
Patient has at least 1 of the following:
 
 1. Purulent drainage from the superficial incision. 2. Organisms isolated from an aseptically-obtained culture of fluid or tissue from the superficial incision. 3. Superficial incision that is deliberately opened by a surgeon, attending physician or other designee and is culture-positive or not cultured 
And
 
Patient has at least 1 of the following signs or symptoms: pain or tenderness; localised swelling; redness; or heat. A negative culture finding does not meet this criterion.
 
 4. Diagnosis of a superficial incisional SSI by the surgeon or attending physician or other designee.
Comment	
There are 2 specific types of superficial incisional SSIs:
 
 a. Superficial Incisional Primary – a superficial incisional SSI that is identified in the primary incision in a patient that has had an operation with 1 or more incisions (eg, C-section incision or chest incision for coronary artery bypass grafting surgery [CBGB]). b. Superficial Incisional Secondary – a superficial incisional SSI that is identified in the secondary incision in a patient that has had an operation with more than 1 incision (eg, donor site incision for CBGB).
Exceptions	
The following do NOT qualify as criteria for meeting the NHSN definition of superficial SSIs:
 
 • A stitch abscess alone (minimal inflammation and discharge confined to the points of suture penetration) • A localised stab wound or pin site infection

	
 • Diagnosis of “cellulitis”, by itself, does not meet criterion d for superficial incisional SSIs 
An infected burn wound is classified as a BURN and is not reportable under this module.

Deep incisional SSI	
Deep incisional SSIs must meet the following criteria:
 
Infection occurs within 30 after the operative procedure (where Day 1 = the procedure date)
 
And
 
Involves deep soft tissues of the incision (eg, fascial and muscle layers)
 
And
 
Patient has at least 1 of the following:
 
 • purulent drainage from the deep incision. • a deep incision that spontaneously dehisces or is deliberately opened by a surgeon, attending physician or other designee and is culture-positive or not cultured. 
And
 
 • patient has at least 1 of the following signs or symptoms: fever (>38°C); localised pain or tenderness. A culture-negative finding does not meet this criterion. • an abscess or other evidence of infection involving the deep incision that is detected on direct examination, during invasive procedure, or by histopathologic examination or imaging test.
Comments	
There are 2 specific types of deep incisional SSIs:
 
 1. Deep Incisional Primary – a deep incisional SSI that is identified in a primary incision in a patient that has had an operation with 1 or more incisions (eg, C- section incision or chest incision for CBGB) 2. Deep Incisional Secondary – a deep incisional SSI that is identified in the secondary incision in a patient that has had an operation with more than 1 incision (eg, donor site incision for CBGB)
Organ/Space SSI	
Organ/Space SSIs must meet the following criteria:
 
Infection occurs within 30 days after the operative procedure (where Day 1 = the procedure date)
 
And
 
Infection involves any part of the body, excluding the skin incision, fascia, or muscle layers, that is opened or manipulated during the operative procedure
 
And
 
Patient has at least 1 of the following:
 
 • purulent drainage from a drain that is placed into the organ/space • organisms isolated from an aseptically-obtained culture of fluid or tissue in the organ/space • an abscess or other evidence of infection involving the organ/space that is detected on direct examination, during invasive procedure, or by histopathologic examination or imaging test.

Comments	Because an organ/space SSI involves any part of the body, excluding the skin incision, fascia, or muscle layers, that is opened or manipulated during the operative procedure, the criterion for infection at these body sites must be met in addition to the organ/space SSI criteria.
----------	---

Statistical Analysis Plan: 3599-001

Study Title: A Randomised Controlled Study to Evaluate the Efficacy and Safety of Fibrin Sealant, Vapour Heated, Solvent/Detergent Treated (FS VH S/D 500 s-apr) Compared to DuraSeal Dural Sealant as an Adjunct to Sutured Dural Repair in Cranial Surgery

Study Number: 3599-001 ClinicalTrials.gov Identifier: NCT02891070

Study Phase: Phase 3

Study Design This study is a phase 3, prospective, controlled, randomized, single-blind (patient) multicenter study to compare effectiveness and safety of FS VH S/D 500 s-apr versus DuraSeal Dural Sealant in a total of 202 evaluable subjects (1:1 randomization) undergoing elective cranial surgery for the treatment of a pathological condition specifically located in the posterior fossa (PF) or supratentorial (ST) regions.

Product Name: FS VH S/D 500 s-apr

Formulation Oxidized cellulose

Statistician: [REDACTED]
Baxter Healthcare
[name]
[name]

Sponsor: Baxter Healthcare Corporation
[name]
[name]

Responsible Medical Officer: [REDACTED]

Final Date: 2017 AUG 10

Version: 2.0

Confidentiality Statement

[REDACTED]

[REDACTED]

Table of Contents

1. SIGNATURE PAGE	4
2. LIST OF ABBREVIATIONS AND DEFINITIONS OF TERMS	5
3. INTRODUCTION	6
4. TRIAL OBJECTIVES	6
4.1 Primary Objectives	6
To evaluate the efficacy of FS VH S/D 500 s-apr compared to DuraSeal Dural Sealant as an adjunct to sutured dural closure.	6
4.2 Secondary Objectives	7
4.3 Exploratory Objectives	7
5. STUDY DESIGN AND CONDUCT CONSIDERATIONS	7
5.1 Study Design	7
5.2 Baseline definition	7
5.3 Sample Size	7
5.3.1 Justification of Non-Inferiority Margin	8
5.4 Randomization Procedure	9
5.5 Efficacy Assessments	9
5.6 Safety Assessments	10
5.7 Completion and Discontinuation	11
6. STUDY POPULATIONS	11
6.1 Subject Disposition	11
6.2 Analysis Populations	12
6.3 Protocol Deviations	12
7. STATISTICAL ANALYSIS	12
7.1 General	12
7.2 Handling of Missing Data	13
7.3 Data Safety Monitoring Board	13
7.4 Interim Analysis	13
7.5 Pooling Strategy for Study Sites	13
7.6 Visit Windows/Unscheduled Visits	14
7.7 Other Issues	14
7.8 Changes to Planned Analyses Described in the Clinical Investigation Plan	14

8. DEMOGRAPHICS AND BASELINE CHARACTERISTICS	14
9. SURGERY DETAILS AND EXPOSURE	14
9.1 Planned Surgery Details	14
9.2 Intraoperative Details	14
9.3 Rescue Therapy Details (listing only).....	16
9.4 Post-operative Clinical Assessment of CSF Leak	16
9.5 Surgical Revision.....	17
